1 BACKGROUND AND STUDY RATIONAL

Approximately 10% of cancer cases in Europe account for hematological malignancies, including leukemias, lymphomas and myelomas. In 2020, 293,775 people in Europe were diagnosed with hematological malignancies, and 148,394 people died¹. Despite advances in drug development and emerging targeted therapies, effective and early diagnosis combined with population screening remains the most powerful tool for fighting cancer. In general, there is an urgent need to have minimally-invasive methods to screen and detect hematological malignancies. For cancer management, these tests are needed to quantify pre-treatment and residual tumor burden to provide useful prognostic information before treatment, to assess molecular response at interim time points and minimal residual disease (MRD) at the end of treatment, and to identify tumor-specific abnormalities when possible.

Bone marrow biopsy, considered the gold standard of multiple myeloma (MM) diagnosis and indicated conditions of other hematological malignancies, provides only a snapshot of the disease at the moment taken and is an invasive method, coming with its risks. However, patients diagnosed with MM and other hematological malignancies require continuous painful follow-up biopsies to monitor the condition, this may indeed lead to avoidance of follow-up visits by patients and subjects at risk of being unwilling to get regular screening. For non-Hodgkin's lymphomas (NHL) and Hodgkin's lymphomas (HL), lymph node biopsy is the gold standard for their diagnosis. Newly developed minimally-invasive diagnostic tools based on liquid biopsy may complement and possibly eventually overcome conventional biopsies. Liquid biopsy can provide real-time feedback on patient condition based on systematic and routine measurements of critical biomarkers - a characteristic that is objectively measured and evaluated as an indicator of normal biological processes or pathogenic processes. Despite extensive progress, research and development are still needed before implementation of liquid biopsy-based tests as the standard of care.

Accumulating evidence shows that epigenetic changes provide unique signatures indicating disease type and stage². These modifications will be detected in genomic DNA extracted from peripheral blood cells, as well as from cell-free and exosomal DNA arising mostly from dying cells, cancer or healthy.

Cancer cells, and specifically hematological tumor cells, undergo dramatic changes in methylation patterns during the tumorigenesis process. For AML, aberration in DNA methylation has been shown to be a key factor in initiation and progression of the disease, and methylation patterns may predict disease outcome³. Alterations in DNA methylation were also observed at early stages of hematological cancers as well as in pre-malignant conditions such as myelodysplastic/myeloproliferative neoplasms (MPN/MDS)^{4,5}. Mutations in DNA methyltransferase 3A (DNMT3A), one of the key mediators responsible for DNA methylation, were found in almost all hematological malignancies at various frequencies with up to 35%, and contribute to the epigenetic aberrations in hematological malignancies⁶. 5-hydroxymethylcytosine (5hmC), the product of demethylation process, was also found to be aberrantly expressed in hematological malignancies and other cancers, and correlate with disease stage and prognosis⁷. Furthermore, in up to 25% of hematological malignancies, the key enzyme TET2, which oxidizes 5mC to 5hmC is mutated, resulting in aberrant 5mC and 5hmC patterns⁸. These aberrant epigenetic modifications can be detected in genomic DNA extracted from peripheral blood of patients with myeloid malignancies⁷. Since cancer cells tend to proliferate at high rates, this process is also accompanied by extensive cell death and elevated representation of tumor DNA in the blood plasma⁹. Thus, methylation and hydroxymethylation patterns in cell-free DNA were shown to indicate cell-of-origin cell death by tissue specific epigenetic signal¹⁰⁻¹². These facts triggered various technologies and assays aimed at probing the genetics, fragment length and methylation signatures of cell-free DNA. It has been already found that monitoring of epigenetic changes provides useful biomarkers for diagnosis and monitoring of cancer, and the first products are already appearing in the market, with Grail Inc. Currently leading the cancer diagnosis domain with a sequencing-based cell-free DNA methylation assay. Most activity in the field is focused on identifying biomarkers using existing methods (mostly sequencing, micro-arrays or QPCR for nucleic acids). Some of these methods suffer from low single-to-noise (SNR) ratio inherently due to the need to sample the entire DNA content and detect the tiny fraction of the relevant DNA population¹³. Other methods suffer from low throughput and/or high costs. SANGUINE introduces a novel platform that is capable of probing thousands of epigenetic DNA markers at high sensitivity and low cost. Preliminary results using the SANGUINE technology have shown that hundreds of loci exhibit detectable differential methylation pattern between hematological malignancies and

healthy control individuals, indicating potential for early diagnosis. Furthermore, different types of hematological malignancies showed differential methylation patterns, a fact that will be utilized for development of an accurate minimally-invasive diagnostic tool for diagnostics as well as disease monitoring.

The circulating Cell-free Genome Atlas (CCGA) study (clinical trial NCT02889978) is an active study that recruited more than 15,000 participants aiming to discover cancer-specific biomarkers in cell-free DNA. Three types of whole genome analysis were adopted, where methylation analysis (performed by whole-genome bisulfite sequencing) outperformed other methods. A mid report presented the ability to recognize multi-cancer types (cross >50 cancer types) at all stages, with specificity of 99.5%, indicating a low false-positive rate of 0.5%. Sensitivity of cancer signal detection increased with higher stages - 16.8% for stage I, 40.4% for stage II, 77% for stage III and 90.1% for stage IV¹⁴.

The STRIVE study (Clinical Trial NCT03085888) is a similar study with ~100,000 participants aiming for biomarker discovery based on methylation analysis in cell-free DNA and included hematological malignancies. A mid report showed 99.5% specificity and increasing sensitivity with higher stage. For all cancer types, sensitivity of the detection of stages I-III was 44.2%, where in 12 high signal cancers including lymphoma, sensitivity for stages I-III was 69.8%¹⁵.

This study aims to develop a minimally-invasive, fast, highly sensitive diagnostics tool for screening, early detection and monitoring of hematological malignancies. This test will enable classification of a broad spectrum hematological malignancies based on detection of epigenetic biomarkers from genomic DNA, cell-free (cf) DNA and exosomal DNA

1.1 HemaChip mechanism of action

It is well established that hematological tumor cells undergo dramatic changes in epigenetic patterns. Results from Tel Aviv University (TAU) show that even bulk measurement of the levels of 5mC and 5hmC in blood of patients with various types of hematological cancers show differential epigenetic pattern between healthy and cancer samples (¹⁶ and unpublished data). Preliminary experiments aiming to map 5mC patterns in blood taken from healthy individuals, multiple myeloma (MM) patients and follicular lymphoma patients (FL) revealed 522 loci differentiating between the three states according to the methylation status. In cell-free DNA from

hematological malignancies patients, MM-associated pattern consisted of 981 loci differentially methylated between healthy and MM patients. For 5hmC, 126 differential loci were recognized between healthy and cancer. In all cases, loci with Z-score of 2 were taken into account. In regards to 5hmC, the relatively low number of differential loci is expected due to the relatively low percentage of 5hmC in genomic DNA. These results strongly support our hypothesis that epigenetic changes can be detected and indicate the existence of different cancer types, not only hematological malignancies types.

1.2 The consortium and JaxBio

The aim of SANGUINE project is to develop a novel tool for early detection and screening of hematological malignancies. The project involves the collection of blood samples from patients diagnosed with various types of hematological cancers or pre-malignant conditions, follow-up patients, individuals at-risk of developing hematological malignancy and control individuals. JaxBio Technologies exclusively licensed the technology and together with TAU developed the discovery approach utilizing commercial microarrays to generate epigenetic biomarkers from genomic as well as cfDNA. This innovative technology is at the basis of the SANGUINE project.

TAU is the coordinator of all clinical aspects of the SANGUINE project.

The SANGUINE consortium consists of four clinical partners from the following medical centers: Tel-Aviv Sourasky Medical Center (TASMC), Israel; University Hospital Olomouc (FNOL), Czech Republic; Vilnius University Hospital Santaros Klinikos (VULSK), Lithuania; National and Kapodistrian University of Athens (NKUA), Greece. Samples will be collected in all four medical centers throughout the project. Other non-clinical partners are: TEL AVIV UNIVERSITY (TAU), Israel; EUROPEAN CANCER ORGANISATION (ECO), Belgium; FZMB GMBH FORSCHUNGSZENTRUM FUR MEDIZINTECHNIK UND BIOTECHNOLOGIE (FZMB), Germany; UNIVERZITA PALACKEHO V OLOMOUCI (UP), Czechia; PREDICTBY RESEARCH AND CONSULTING S.L. (PBY), Spain; JAXBIO TECHNOLOGIES LTD (JAX), Israel and UAB ORIENTOS (Orientos), Lithuania.

The SANGUINE project was awarded by the European Commission under Horizon Europe (Project 101097026 — SANGUINE).

The results of this study may be used by JaxBio for future regulatory marketing approvals in Europe and in the US. All partners will have the access to the anonymized data.

2 STUDY OBJECTIVES

The primary and the secondary objectives of this clinical trial are defined as follows:

Primary objectives:

1. Biomarker discovery - define a set of differential epigenetic biomarkers that uniquely identify the following conditions: MM, pre-MM conditions [smoldering MM (SMM) and monoclonal gammopathy of undetermined significance (MGUS)], HL, aggressive NHL [diffuse large B cell lymphoma (DLBCL), FL, MZL, AML, MDS and control subjects with no malignant disease .
2. Validation – validating the discovery platform (HemaChip) as a diagnostic tool for various hematological malignancies.
3. Towards early detection - Patients, at risk of relapse tested periodically to evaluate early detection capability of the HemaChip.
4. Towards population screening - evaluate the sensitivity and specificity for screening in populations at risk for developing the investigated cancers: (i) elderly (>65 years old) at high risk to develop MM; (ii) first degree relatives of the conditions described above.

Secondary objectives:

1. Evaluate the correlation between epigenetic status and well-known prognostic markers, including known genetic markers.
2. Predict response to therapy.

Exploratory objectives:

1. Identify new therapeutic targets based on epigenetically modified genomic loci.
2. Provide prognostic information at pre-treatment and monitoring of MRD.

3 ENDPOINTS

Primary endpoints:

1. Define a set of biomarkers for each condition. Determine efficiency, sensitivity, specificity, limit of detection.
2. Determine assay efficiency, sensitivity, specificity, limit of detection for each stage.

Secondary endpoints:

1. Determine prognostic value of discovered epigenetic markers.
2. Determine metrics for response to therapy.

Exploratory endpoints:

1. Identify therapeutic targets base on differential epigenetic loci.
2. Determine an MRD protocol for epigenetic follow-up.

4 STUDY DESIGN

This is a multi-center, open-label, non-interventional controlled study to identify and characterize the epigenetic signatures for a set of hematological malignancies.

Subjects will be screened for eligibility and then, after signing an Informed Consent Form, the first peripheral blood will be obtained.

Periodical blood samples will be obtained from the participants. Relapse patients will have their retrospective blood samples analyzed to identify early signs of disease.

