4.2 Second stage

In the second stage, at least 250 patients with MM and 250 patients with NHL and at least 100 patients with each of the remaining hematological malignancies mentioned above will be tested.

Out of these patients, AML, lymphoma and MM patients will be followed-up at the clinical sites. Periodic sampling will be defined according to disease type and progression rate. Blood and plasma samples will be stored in the clinical sites until relapse diagnosis. At this stage, blood samples will be analyzed retrospectively on the HemaChip. The screening, enrollment and samples collection can begin in the first stage of the trial, in order to allow a maximum follow-up period for at-risk subjects as part of the study, and to meet the recruitment goals.

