6.2 Schedule of events

The detailed summary of the evaluations and procedures planned in this study is presented in Tables 2 and 3.

Table 2. Schedule of events

Evaluation	Screening visit¹ (Day -28 to -1)	Baseline sample (Day 1 ± 28 days)	Follow-up visit² (sub-set of patients in Stage 2)
Signed consent form	X		
Assessment of eligibility criteria	X		
Assigning patient ID	X		
Assigning patient barcode	X		
Record medical history ³	X	X	
Record concomitant medications	X	X	X
Record demographics ⁴	X		
Record smoking history / status	X	X	X
Record prior anti-cancer treatments ⁵	X	X	
Record weight	X	X	X
Record heights	X		
Record baseline disease characteristics including prognostic profile ²	X		
MM lab profile for subjects at risk to develop the investigated hematological malignancies ⁶	X		
Blood sampling for central lab (JaxBio) ⁷		X ²	X ²
Disease response evaluation			X ²
Survival status			X
Record adverse events		X	X

¹ Screening visit can be performed at the same day as baseline sample.

² Refer to Table 3 for recommended schedule and disease assessment plan for follow-up patients in Stage 2.

³ Medical history will include details of initial diagnosis.

⁴ Demographics include sex, age and race.

⁵ Only for Secondary-AML, transformed FL and MZL conditions.

⁶ **In Stage 3.** MM lab profile will include SPEP and FLC, full chemistry and CBC.

⁷ Two (2) blood tubes for each sample will be collected and shipped. Refer to Study Manual.

HemaChip tests at the clinical sites ⁸		X ⁹	X ⁹
---	--	----------------	----------------

⁸ **In stages 2 and 3 of the clinical trial only.** The HemaChip and custom reagents will be distributed to partners' labs and all tests will be conducted at the clinical sites.

⁹ Two (2) blood tubes for each sample will be collected. One (1) for test at the clinical sites and the second as a backup for additional validation tests at JaxBio and TAU, as needed. Refer to Study Manual.

Table 3. Recommended schedule and disease assessment plan – Only for follow-up patients

Condition Visit	Baseline Characteristics and Assessments ¹	Follow-up for Disease Evaluation		Blood Sample for Central Lab/HemaChip at site ^{2,3}
		Disease Evaluation ¹	Recommended Schedule	

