7.2 Baseline sample

- Review medical history
- Review concomitant medications
- Review prior anti-cancer treatments
- Record weight
- Record smoking status
- Blood sampling for central lab (JaxBio). Two (2) blood tubes for each sample will be collected and shipped. Refer to study manual.
- Record AEs
- Hemachip tests at the clinical sites - **in stages 2 and 3 of the clinical trial only**. Two (2) blood samples will be collected. One (1) for testing at the clinical sites and the second as a backup for additional validation tests at JaxBio and TAU, as needed. Refer to Study Manual.

7.3 Clinical follow-up – sub-set of patients in Stage 2

- Review concomitant medications
- Record weight
- Record smoking status
- Blood sampling for central lab (JaxBio) - refer to Table 3 for recommended schedule and disease assessment plan. Refer to study manual.

- Record AEs
- Disease response evaluation (for follow-up patients in Stage 2) - refer to Table 3 for recommended schedule and disease assessment plan
- Survival status
- Hemachip tests at the clinical sites - **in stages 2 and 3 of the clinical trial only**. Two (2) blood samples will be collected. One (1) for testing at the clinical sites and the second as a backup for additional validation tests at JaxBio and TAU, as needed. Refer to Study Manual.

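### The protocol gives two conflicting rules for reading serial follow-up samples; under the relapse-triggered rule, early relapse detection has no non-relapsing comparison

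*Protocol*

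**What the plan says.** The design text ties the reading of stored samples to relapse. Section 4 of the Protocol states: "Relapse patients will have their retrospective blood samples analyzed to identify early signs of disease". Section 4.2 adds: "Blood and plasma samples will be stored in the clinical sites until relapse diagnosis", and continues: "At this stage, blood samples will be analyzed retrospectively on the HemaChip". The synopsis, under Methodology, repeats both. No section commits to reading the stored samples of patients who do not relapse, and none names a comparison series.

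The schedule reads differently. Table 2 in Section 6.2 has a row "HemaChip tests at the clinical sites", marked at baseline and at the follow-up visit of the Stage 2 subset. Section 7.3 lists the same test at follow-up. The tube rule, worded alike in Sections 7.2 and 7.3, is: "One (1) for testing at the clinical sites and the second as a backup for additional validation tests at JaxBio and TAU, as needed". Neither place makes the test conditional on relapse.

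Primary objective 3 in Section 2 is: "Patients, at risk of relapse tested periodically to evaluate early detection capability of the HemaChip". Primary endpoint 2 in Section 3 is: "Determine assay efficiency, sensitivity, specificity, limit of detection for each stage".

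**The concern.** Which samples go on the chip fixes what can be estimated later. An analysis plan cannot recover specificity from assays that were never run, so this is a protocol matter and not one to leave to the SAP.

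If sites follow Sections 4 and 4.2, every serial sample that is read comes from someone already known to have relapsed. There is then no series in which a negative result would be correct throughout follow-up. A positive before relapse could be early signal, residual treated disease, a storage effect or background positivity, and the data could not separate these. If sites follow Table 2 and Section 7.3, the comparison exists. Four clinical centres applying different rules would produce series that cannot be pooled cleanly.

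**Working it through.** **The plan's own figure.** The Protocol gives no sample size or expected number of relapses for objective 3. The nearest figure is the validation-stage 356 in Section 10.4 (85% against 80%, arcsine method, significance level 0.05, power 0.8). One-sided: n = [(1.645 + 0.842) / (2·asin√0.85 − 2·asin√0.80)]² = 355.4, so 356. The figure reproduces, but it concerns diagnostic validation and says nothing about relapse.

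**The two rules side by side.**

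| | Sections 4, 4.2 and synopsis | Table 2, Section 7.3 |
|---|---|---|
| When read | after relapse diagnosis, from storage | at follow-up visits |
| Whose samples | relapse patients | the Stage 2 follow-up subset, relapsing or not |
| Non-relapsing series read | none stated | yes |

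**Can another group supply the comparison?** No. Section 4.4 has controls and Stage 3 subjects donating once, so they provide no serial samples. They are also not treated patients in follow-up.

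**Can visit-time testing cover every sample?** Not as samples are drawn. Section 4.2 and the footnote to Table 1 allow collection to begin during the first stage, while Section 8 places development of the HemaChip in years 2-3. Follow-up samples drawn before the chip exists can only be read from storage, and the only stated trigger for that is relapse.

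**Scale of chance positives (illustration).**

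Inputs from Table 3: MM every 2 months, so m = 12/2 = 6 samples in a year; lymphoma every 3 months in the first two years, so m = 12/3 = 4. AML is left out because its visits depend on treatment.

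Assumptions, none of them from the Protocol: per-sample false-positive rate f of 2%, 5% or 10%; independent visits; all samples disease-free.

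Formula: P(at least one positive) = 1 − (1 − f)^m.

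| f | MM, m = 6 | Lymphoma, m = 4 |
|---|---|---|
| 2% | 1 − 0.98⁶ = 0.114 | 1 − 0.98⁴ = 0.078 |
| 5% | 1 − 0.95⁶ = 0.265 | 1 − 0.95⁴ = 0.185 |
| 10% | 1 − 0.90⁶ = 0.469 | 1 − 0.90⁴ = 0.344 |

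Positive correlation between a patient's visits would lower these values. Samples that hold active or residual disease fall outside the calculation, because a positive there is not false.

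**The case against.** The strongest reply is that the relapse-triggered rule is not the whole document. Sections 4 and 4.2 say what happens to relapsers' samples; they do not say that other samples go unread. Table 2, Section 7.3 and the periodic testing in objective 3 all point to reading at visits whatever the outcome. This stands. A reader might infer that only relapsers' samples will ever be read, and the documents do not support that.

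A reader might also infer that objective 3 cannot be answered at all. That goes too far even under the relapse-triggered rule. The objective asks about early detection capability and, unlike objective 4, does not name specificity. Detection among relapsers and its timing before relapse could still be described, and a patient's own earlier samples give a limited internal reference. The per-stage wording of endpoint 2 can be met for diagnosis from the controls in the interim comparison of Section 10.3. What is lost is specificity, false-alarm rate and predictive value for relapse.

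Finally, a reader might infer that false alarms would be credited as early detection. The Protocol defines no early-detection event. A single positive, a confirmed positive or a rising trend all remain open, and the definition may sit in the SAP. The supported statement is that chance positives could not be distinguished from early detection.

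The reply does not remove the contradiction. Nor does it supply a rule for the stored samples of non-relapsers, including those drawn before the chip is available.

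**Conclusion.** The concern holds as a contradiction with a conditional consequence. The Protocol states two incompatible rules for when and for whom serial follow-up samples are read. If the relapse-triggered rule is applied, relapse-specific specificity, false-alarm rate and predictive value cannot be estimated for a primary objective. If the schedule in Table 2 and Section 7.3 is applied, they can be.

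The contradiction and the missing comparison rest on the text alone. The percentages rest on the assumed error rates, independence and disease-free samples; they show scale and are not Protocol values. The matter should be settled before chips are allocated or stored samples are discarded, because the loss could not be repaired at analysis.

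**What to change.** Reconcile the synopsis and Sections 4 and 4.2 with Table 2 and Section 7.3 into one reading rule under which non-relapsers' samples are also read. There are two workable forms.

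1. Read all follow-up samples, as Table 2 and Section 7.3 already schedule, and state that samples drawn before the chip exists are read from storage whatever the outcome.
2. Read relapsers' samples together with those of non-relapsing patients matched on disease, follow-up time and storage time, in the same batch and with relapse status withheld from the reader. Record the sampling fractions, because false-alarm rate and predictive value come from a matched subset only by weighting.

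As a planning guide with assumed numbers, 100 non-relapsers of whom 95 are negative would give an exact 95% interval for specificity of 0.887 to 0.984; 50 with 48 negative would give 0.863 to 0.995.

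**Cost.** No new visits or patients are needed, since note 3 to Table 3 already has blood taken at every disease-evaluation visit. The cost is additional chips, and none beyond plan if Table 2 is the operative rule. If it is not, reading everything is the dearer form: for MM the ceiling is 250 patients × 18 visits (36 months / 2) = 4,500 tests. The true number would be lower, because Section 4.4 limits follow-up to a subset whose size is not given.
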